#### 4.1.5 Blinding and procedures for unblinding

##### 4.1.5.1 Blinding

This open-label trial will be treated as blinded by the sponsor until primary analysis database lock.

The Data Monitoring Committee (DMC) will be provided with unblinded data in order to ensure the ongoing safety and efficacy of the trial. Data unblinding as required for the DMC review will be conducted on an ongoing basis by a data manager or CRO not involved in the trial in order to keep the trial team blinded.

For the primary analysis of PFS, the trial team will complete the aggregate analysis.

##### 4.1.5.2 Procedures for emergency unblinding

Not applicable.

#### 4.1.6 Packaging, labelling, and re-supply

Details of packaging and sample labels will be found in the Investigator Study File (ISF).

Trial drug packages will have unique medication numbers which will be used for tracking purposes only. The medication numbers will not be linked to randomisation numbers.

Afatinib will be supplied as film-coated Tablets. Available dosage strength will be 20 mg, 30 mg, 40 mg, and 50 mg. Tablets will be supplied in child-resistant, tamper-evident bottles.

Erlotinib will be supplied as film-coated Tablets. Available dosage strength will be 25 mg, 100 mg, and 150 mg. Tablets will be supplied in child-resistant bottles in the US and Canada. For all other countries, erlotinib will be supplied in polyvinyl chloride (PVC) blister sealed with aluminium foil.

Resupply of all study medication will be managed by the IXRS system. Details are provided in the ISF and IXRS User Guides.

#### 4.1.7 Storage conditions

Trial medication, which will be provided by the sponsor and/or a CRO appointed by the sponsor, must be kept in a secure, limited access storage area under the storage conditions defined below until supplied/administered to patient. Temperature logs must be maintained to make certain that the drug supplies are stored at the correct temperature. In case temperature would be out of range, this has to be reported in the ISF and the sponsor be notified.

##### 4.1.7.1 Storage conditions for afatinib

Afatinib must be stored in the original package in order to protect from light. Film-coated Tablets are humidity-sensitive; therefore, bottles must be kept tightly closed to protect from moisture. Tablets must be stored according to the instructions on the label.

Patients should be instructed to keep the bottles tightly closed to protect from moisture.

##### 4.1.7.2 Storage conditions for erlotinib

Erlotinib must be stored in the original packaging according to the instructions on the label.

If the erlotinib storage conditions are found to be outside the specified range, contact the local clinical monitor as provided in the list of contacts.

#### 4.1.8 Drug accountability

Drug supplies, which will be provided by the sponsor or CRO appointed by the sponsor, must be kept in a secure, limited access storage area under the storage conditions defined by the sponsor. A temperature log (documenting at least a weekly min/max temperature reading) at

**Proprietary confidential information.**

© 2016 Boehringer Ingelheim International GmbH or one or more of its affiliated companies. All rights reserved.

This document may not - in full or in part - be passed on, reproduced, published or otherwise used without prior written permission.

the study site must be maintained to make certain that the drug supplies are stored at the correct temperature.

The investigator / pharmacist / investigational drug storage manager will receive the investigational drugs delivered by the sponsor or CRO when the following requirements are fulfilled:

- approval of the study protocol by the IRB / ethics committee,
- availability of a signed and dated clinical trial contract between the sponsor and the Head of Trial Centre,
- approval/notification of the regulatory authority, e.g. competent authority,
- availability of the curriculum vitae of the principal investigator,
- availability of a signed and dated clinical trial protocol or immediately imminent signing of the clinical trial protocol, if permitted by local regulations.
- All other local requirements are met (i.e. submission of completed, signed Form 1572 in the US)

The investigator / pharmacist / investigational drug storage manager must maintain records of the product's delivery to the trial site, the inventory at the site, the use by each patient, and the return to the sponsor or alternative disposition of unused product(s).

These records will include dates, quantities, batch/serial numbers, expiry ('use by') dates, and the unique code numbers assigned to the investigational product(s) and trial patients. The investigator / pharmacist / investigational drug storage manager will maintain records that document adequately that the patients were provided the doses specified by the CTP and reconcile all investigational product(s) received from the sponsor. At the time of return to the sponsor or appointed CRO, the investigator / pharmacist / investigational drug storage manager must verify that all unused or partially used drug supplies have been returned by the clinical trial patient and that no remaining supplies are in the investigator's possession.

## **4.2 CONCOMITANT THERAPY, RESTRICTIONS, AND RESCUE TREATMENT**

### **4.2.1 Rescue medication, emergency procedures, and additional treatments**

#### Rescue medication

Rescue medications to reverse the actions of afatinib are not available. There is no specific antidote for overdose with afatinib. Potential adverse events should be treated symptomatically. Common adverse events of treatment with afatinib include diarrhoea, nausea, vomiting, rash/acne and stomatitis. To improve tolerability and the probability of clinical benefit, patients should receive prompt and appropriate supportive care at the first signs of symptoms. Suggested treatments for AEs are described below.

#### Concomitant treatments

**Proprietary confidential information.**

© 2016 Boehringer Ingelheim International GmbH or one or more of its affiliated companies. All rights reserved.

This document may not - in full or in part - be passed on, reproduced, published or otherwise used without prior written permission.

Concomitant medications or therapy to provide adequate supportive care may be given as clinically necessary.

After randomization, palliative radiotherapy may be initiated for bone pain or for other reasons (e.g. bronchial obstruction, skin lesions), provided that the total dose delivered is in a palliative range according to institutional standards. The irradiated area can not be used for tumour response assessment. During palliative radiotherapy, study treatment should be held and may be resumed once the patient has recovered from any radiation associated toxicity. If the medication is interrupted for more than 14 days, the decision to continue will be made by the investigator in agreement with the BI Clinical Monitor. Continuous dose interruption of >28 days due to palliative radiotherapy is not allowed.

All concomitant therapy, including anaesthetic agents, vitamins, homeopathic/herbal remedies, nutritional supplements, must be recorded in the eCRF during the screening and treatment period, starting with any medications taken within 4 weeks of the screening visit, and ending at the EOT visit. After the EOT visit, only concomitant therapy indicated for treatment of an AE has to be reported.

In case of major surgery (as judged by the investigator), it is recommended to stop treatment with afatinib around one week prior to the surgery, and to restart treatment after complete wound healing. If the medication is interrupted for more than 14 days, the decision to continue medication will be made by the investigator in agreement with the BI Clinical Monitor.

Refer to the Tarceva® SPC/PI included in the site ISF for management of AEs due to treatment with erlotinib.

### Emergency procedures

For patients receiving either afatinib or erlotinib, careful assessment of all patients with an acute onset and/or unexplained worsening of pulmonary symptoms (dyspnoea, cough, fever) should be performed to exclude interstitial lung disease (ILD). Study drugs should be interrupted pending investigation of these symptoms. If interstitial lung disease is diagnosed, study drug must be permanently discontinued and appropriate treatment instituted as necessary. Refer to Tables [4.1.4.1.2: 1](#) and [4.1.4.2.1:1](#) for details.

Emergency contact information is provided in the ISF.

## **4.2.2 Restrictions**

### 4.2.2.1 Restrictions regarding concomitant treatment

Concomitant medications, or therapy to provide adequate supportive care, may be given as clinically necessary.

Palliative radiotherapy may be given as described in [Section 4.2.1](#).

**Proprietary confidential information.**

© 2016 Boehringer Ingelheim International GmbH or one or more of its affiliated companies. All rights reserved.

This document may not - in full or in part - be passed on, reproduced, published or otherwise used without prior written permission.

Patients receiving erlotinib and taking warfarin or other coumarin-derivative anticoagulants should be monitored regularly for changes in PT and INR.

Additional experimental anti-cancer treatment and/or standard chemo-, immunotherapy, hormone treatment; with the exception of bisphosphonates (denosumab is excluded), megestrol acetate and use of anti-androgens and/or gonadorelin analogues for treatment of prostate cancer; or radiotherapy (other than palliative radiotherapy for symptom control) is not allowed concomitantly with the administration of study treatment.

### Erlotinib

Erlotinib is metabolized predominantly by CYP3A4, and inhibitors of CYP1A2 would be expected to increase exposure to the drug. Caution should be used during co-treatment with erlotinib and CYP3A4 inhibitors, and in some situations a decreased dose of erlotinib may be required. CYP3A4 inducers may increase clearance of erlotinib. See [Appendix 10.6](#) for a list of common CYP3A4 inhibitors and inducers. Alternate treatments should be considered. If an alternate treatment is not possible, erlotinib dose modifications should be considered.

Grapefruit and grapefruit juice can reduce the availability of CYP3A4 enough to significantly increase the bioavailability of drugs metabolized by CYP3A4 ([P04-06229](#)).

St. John's Wort increases the activity of CYP3A4, effectively decreasing the bioavailability of drugs metabolized by the same system.

Erlotinib is metabolized to a lesser extent by CYP1A2. Caution should be used during co-treatment with erlotinib and CYP1A2 inhibitors, and in some situations a decreased dose of erlotinib may be required ([R11-1186](#)).

Co-administration of erlotinib with omeprazole, a proton pump inhibitor, decreased the erlotinib AUC. The concomitant use of proton pump inhibitors should be avoided if possible.

Co-administration of erlotinib with ranitidine, an H2 receptor antagonist, decreased the erlotinib AUC. Erlotinib and any H2 receptor antagonist should be taken in a staggered manner. Erlotinib must be taken once a day 10 hours after the H2 receptor antagonist dosing and at least 2 hours before the next dose of H2 receptor antagonist.

Refer to [Appendix 10.6](#) and the Tarceva® SPC or PI included in the ISF for more information.

#### 4.2.2.2 Restrictions on diet and life style

Patients receiving either afatinib or erlotinib should be advised to avoid intense irradiation with UV light and harsh detergents to prevent skin related adverse events.

Patients receiving afatinib or erlotinib should be advised to avoid any foods known to aggravate diarrhoea.

Suggest patients receiving afatinib or erlotinib use a thick, alcohol-free cream on dry areas of the body.

#### 4.2.2.3 Women of child-bearing potential and pregnancy prevention

Patients who are not of child-bearing potential due to being postmenopausal (1 year without menstruations and at least 2 years without menstruation following chemotherapy) ([R11-1406](#)) or surgical sterilization (oophorectomy, hysterectomy and/or tubal ligation) do not need to use contraception to be eligible for participation in this trial.

All other patients are considered to have child-bearing potential and must use adequate contraception while participating in this trial (from screening until end of trial participation or 2 months after last dose of trial medication, whichever is later).

Acceptable methods of birth control include surgical sterilization or double barrier method, and must be in accordance with local regulations where applicable. Double barrier method of contraception is defined as two barrier methods used simultaneously each time the patient has intercourse. Acceptable barrier methods include diaphragm, female condom, cervical cap, male condom, and intrauterine device (IUD) (the diaphragm and cervical cap must be used in conjunction with spermicidal jelly/cream). Those using hormonal contraceptives, or with partners using hormonal contraceptives, must also be using an additional approved method of contraception (as described above). Partner vasectomy, natural “rhythm”, and spermicidal jelly/cream are not acceptable methods of contraception.

Women who become pregnant while participating in the study must discontinue study medication immediately. The pregnancy must be reported following procedures detailed in [Section 5.2.2.2](#).

#### 4.2.3 Management of expected adverse events

Dermatologic adverse events and diarrhoea are the most common side-effects associated with treatment with afatinib. Treatment of these side-effects should be proactive and should be started as early as possible after onset of symptoms.

The most common adverse events in NSCLC patients receiving erlotinib are rash and diarrhoea, anorexia, fatigue, dyspnea, cough, nausea, infection and vomiting ([R11-1186](#)). Refer to the Tarceva package insert for management of these events.

#### 4.2.3.1 Management of diarrhoea and hydration status

Diarrhoea occurs at a high frequency and generally begins within 2 weeks of exposure to afatinib. Although usually mild to moderate, diarrhoea may lead to dehydration and compel treatment modification or discontinuation, so early management is essential ([Table 4.2.3.1: 1](#)). At the time of initiation of treatment with afatinib, site staff should ensure patients are counseled on prompt reporting of any diarrhoea and instituting corrective measures such as hydration and treatment with antidiarrhoeals. Sites should confirm that a patient has ready access to antidiarrhoeal medication.

Patients must be advised to drink an adequate amount of fluids to make up for the fluid lost through diarrhoea.

**Proprietary confidential information.**

**© 2016 Boehringer Ingelheim International GmbH or one or more of its affiliated companies. All rights reserved.**

This document may not - in full or in part - be passed on, reproduced, published or otherwise used without prior written permission.

Table 4.2.3.1: 1 Grade specific treatment of study-drug related diarrhoea

Severity (CTCAE Grading)	Description	Intervention concerning afatinib treatment	Specific intervention
Mild (Grade 1)	Increase of < 4 stools per day over baseline; mild increase in ostomy output compared with baseline	Continue same dose	Stop laxatives and advise patient to drink at least 8-10 glasses of clear fluids per day; 4 mg (2 Tablets) of loperamide to be taken immediately, followed by 2 mg (1 Tablet) after each loose stool until bowel movements cease for 12 hours
Moderate (Grade 2)	Increase of 4-6 stools per day over baseline; iv. fluids indicated < 24 hours; moderate increase in ostomy output compared with baseline; not interfering with ADL	Continue same dose unless Grade 2 diarrhoea continues for <math>\geq 2</math> days (48 hours) in which case treatment must be interrupted until recovered to $\leq$ Grade 1 followed by dose reduction	Continue loperamide; assess for dehydration and electrolyte imbalance; consider iv fluids and electrolyte replacement
Severe (Grade 3)	Increase of $\geq 7$ stools per day over baseline; incontinence; iv fluids > 24 hours; hospitalization; severe increase in ostomy output compared with baseline; interfering with ADL	Dose interruption until recovered to $\leq$ Grade 1 followed by dose reduction 	See Grade 2; plus: an infectious process should be ruled out with stool cultures; aggressive iv fluid replacement $\geq 24$ hours; hospitalization to monitor progress; consider prophylactic antibiotics if patient is also neutropenic;
Life threatening (Grade 4)	Life-threatening consequences (e.g. haemodynamic collapse)	Dose interruption until recovered to $\leq$ Grade 1 followed by dose reduction 	See Grade 3

If despite optimal supportive care and a treatment interruption, diarrhoea does not resolve to CTC AE Grade  $\leq 1$  within 14 days, treatment with afatinib must be permanently discontinued.

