**Proprietary confidential information.**

© 2016 Boehringer Ingelheim International GmbH or one or more of its affiliated companies. All rights reserved.

This document may not - in full or in part - be passed on, reproduced, published or otherwise used without prior written permission.

Table 4.1.4.1.2: 1 Dose reduction scheme for afatinib

AE type and CTCAE Grade	Action	Dose reduction scheme

Events related to study drug:
 
 
• Diarrhoea Grade 2 persisting for 2 or more consecutive days (48 hours) despite adequate anti-diarrhoeal medication/hydration
 
• Nausea and/or Vomiting Grade 2 persisting for 7 or more consecutive days despite anti-emetic treatment/hydration
 
• Reduced renal function to <math>\geq</math> Grade 2 as measured by serum creatinine, proteinuria or decrease in glomerular filtration rate of more than 50% from baseline
 
• Any drug related AE Grade <math>\geq</math>3
 
	
Pause treatment until patient has recovered to Grade <math>\leq</math>1 or baseline.
 
Resume treatment at reduced dose according to schedule opposite.
 
If patient has not recovered to Grade <math>\leq</math>1 or baseline within 14 days study treatment must be permanently discontinued.
	
If patient was receiving 50 mg, resume treatment at a dose of 40 mg.
 
If patient was receiving 40 mg, resume treatment at a dose of 30 mg.
 
If patient was receiving 30 mg, resume treatment at a dose of 20 mg.
 
If patient was receiving 20 mg, discontinue afatinib.

Acute onset and/or unexplained worsening of pulmonary systems (dyspnea, cough, fever)
	
Pause afatinib while clinical assessment to exclude ILD is completed.
	
If ILD is ruled out as a cause of symptoms, grade symptoms and relatedness and report as AEs.
 
If AEs are not related, resume afatinib at current dose. If AEs are drug related, follow directions in row above.
 
If ILD is confirmed, discontinue afatinib

 Baseline is defined as the CTCAE Grade at the start of treatment

 In the event that the patient is deriving obvious clinical benefit according to the investigator's judgement, further treatment with afatinib will be decided in agreement between the sponsor and the investigator.

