Acute onset and/or unexplained worsening of pulmonary systems (dyspnea, cough, fever)	Pause erlotinib while clinical assessment to exclude ILD is completed.	
If ILD is ruled out as a cause of symptoms, grade symptoms and relatedness and report as AEs.
 
If AEs are not related, resume erlotinib at current dose. If AEs are drug related, follow directions in row above.
 
If ILD is confirmed, discontinue erlotinib.

\* Patients taking erlotinib with an inhibitor of both CYP3A4 and CYP1A2 and experiencing a severe adverse reaction should be evaluated for a dose reduction of erlotinib.

 Baseline is defined as the CTCAE Grade at the start of treatment

 In the event that the patient is deriving obvious clinical benefit according to the investigator's judgement, further treatment with erlotinib will be decided in agreement between the sponsor and the investigator.

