## 5.2 SAFETY

### 5.2.1 Endpoints of safety

Safety of afatinib and erlotinib will be evaluated by intensity and incidence of adverse events, graded according to NCI CTCAE version 3.0 ([R04-0474](#)). Safety endpoints include:

- The overall incidence and intensity of adverse events
- Gastrointestinal events (vomiting, nausea, diarrhoea)
- Skin reactions (rash, acne)

Tolerability of afatinib and erlotinib will be assessed based on dosage reduction and discontinuation due to adverse events.

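### For Grade 3-4 diarrhoea on afatinib unresolved at 14 days, one protocol table requires permanent discontinuation without exception and another allows continuation by agreement; the protocol does not say which prevails.

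*Protocol*

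**What the plan says.** **Diarrhoea management table (Protocol Section 4.2.3.1, Table 4.2.3.1: 1).** For Grades 3 and 4 the table calls for interruption until recovery to Grade 1 or less, then a reduced dose. Both rows carry footnote 1: if diarrhoea has not resolved to that level in 14 days, "treatment with afatinib must be permanently discontinued". No exception is given. The Grade 2 row, for diarrhoea lasting 48 hours or more, also requires interruption ("in which case treatment must be interrupted until recovered to" Grade 1 or less) but carries no footnote marker.

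**Afatinib dose-reduction table (Protocol Section 4.1.4.1.2, Table 4.1.4.1.2: 1).** This table names persistent Grade 2 diarrhoea and covers Grade 3-4 diarrhoea through its entry for any drug-related event of Grade 3 or higher. Its default matches: without recovery "within 14 days study treatment must be permanently discontinued". That default is marked with footnote 2. Under it, if the patient is "deriving obvious clinical benefit according to the investigator's judgement", then "further treatment with afatinib will be decided in agreement between the sponsor and the investigator".

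**Erlotinib (Protocol Table 4.1.4.2.1: 1, footnote 2).** The same exception is given: "further treatment with erlotinib will be decided in agreement between the sponsor and the investigator".

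**Use of the data (Protocol Section 5.2.1).** "Tolerability of afatinib and erlotinib will be assessed based on dosage reduction and discontinuation due to adverse events". SAP Section 7.8.1 plans a separate table of adverse events leading to treatment discontinuation.

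**The concern.** Both footnotes are in the current protocol, and they give different instructions at day 14 for the same afatinib patient. The table written specifically for diarrhoea closes off continuation; the general toxicity table leaves it open. An investigator treating severe diarrhoea would naturally turn to the diarrhoea table and would find nothing there to suggest that an exception exists elsewhere.

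The first thing at stake is safety: two patients with the same unresolved severe toxicity could be managed differently because of the page consulted. The second is consistency of measurement. Discontinuation due to adverse events is a stated tolerability measure for both arms, so a stopping rule that reads two ways adds avoidable variation to it.

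**Working it through.** No sample size, event count or power figure is involved, so the check is a comparison of texts.

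**Step 1. Do the two rules apply to the same event?**

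| Feature | Table 4.2.3.1: 1, footnote 1 | Table 4.1.4.1.2: 1, footnote 2 |
|---|---|---|
| Drug | Afatinib | Afatinib |
| Event | Study-drug-related diarrhoea; marker on Grade 3 and 4 rows | Drug-related events, including any of Grade 3 or higher |
| Time limit | 14 days | 14 days |
| Recovery level | Grade 1 or less | Grade 1 or less, or baseline |
| Default at the limit | Permanent discontinuation | Permanent discontinuation |
| Exception | None | Obvious clinical benefit plus sponsor-investigator agreement |

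For Grade 3-4 diarrhoea they overlap fully, and the material difference is the last row. For Grade 2 the position is less clear: the text of footnote 1 names no grade, but its marker is absent from that row. The clear conflict is therefore limited to Grades 3-4.

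**Step 2. Does any other text settle which rule prevails?**
- Protocol Section 3.1 says that study drug dose is modified as in Section 4.1.4 when adverse effects are managed.
- Section 3.3.4.1, reason 5 for stopping study drug, refers to Section 4.1.4.
- Section 4.1.4.1.2 sends treatment-related afatinib toxicities to its own table.
- The paragraph after that table, on longer interruptions, deals with events unrelated to study drug, so it does not apply.
- Section 4.2.3.2 (skin) and Section 4.2.3.3 (mucositis/stomatitis, including its table) refer dose adjustment to Section 4.1.4.
- Section 4.2.3.1 (diarrhoea) contains no such reference and states its own mandatory stopping rule.

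The first three items suggest that Section 4.1.4 governs. None says that it overrides Section 4.2.3.1, and the missing cross-reference in the diarrhoea section leaves the question open.

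**Step 3. Which analyses could be touched?**
- Adverse events leading to discontinuation: yes, in a descriptive table (SAP Section 7.8.1).
- PFS: not directly. Protocol Section 3.1 keeps patients who stop for toxicity under tumour assessment, and efficacy is analysed in all randomised patients (Protocol Section 7.3.1; SAP Section 6.3).

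**Step 4. Can the number of patients be sized?** It would be the product of four quantities: afatinib patients (398 in the synopsis), the rate of drug-related Grade 3-4 diarrhoea, the fraction unresolved at 14 days, and the fraction of those with obvious clinical benefit and sponsor agreement. The documents give no value for the last two, so no count follows.

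**The case against.** The best counter-argument is that precedence is strongly indicated. Three sections direct dose modification to Section 4.1.4, and Section 4.2.1 introduces the supportive-care material as suggested treatment. The default is also identical in both tables, and the exception needs the sponsor's agreement, so a site cannot invoke it alone. Most of this stands, and it makes the problem narrower. It does not remove it: footnote 1 is worded as an obligation, no text ranks the tables, and an agreement reached under footnote 2 would authorise what footnote 1 forbids.

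Stronger readings are tempting but are not supported:
- **A patient count.** A reader might apply the 24.2% Grade 3 diarrhoea rate in Section 4.1.3. That rate comes from patients who started at 50 mg. Here all afatinib patients start at 40 mg, for which the same section reports 6.7% in 30 patients, and escalation requires the absence of diarrhoea in Course 1. Neither rate says how many fail to recover in 14 days.
- **A second conflict over recovery to baseline.** Exclusion criterion 7 bars diarrhoea of Grade 2 or higher, so baseline should already be Grade 1 or less and the added words should rarely matter.
- **Violation code C1 being impossible to apply.** SAP Section 6.2 calls the codes a working list of potentially important violations to be finalised at the blinded meeting, and defines no per-protocol set. The code removes nobody from an analysis.
- **A proven one-arm bias.** The protocol has no competing erlotinib diarrhoea table, but Sections 4.2.1 and 4.2.3 send erlotinib adverse-event management to the product labelling, which is not among the documents.

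**Conclusion.** The contradiction is real and the protocol is wrong as written on this point. For drug-related Grade 3-4 diarrhoea on afatinib not recovered to Grade 1 or less in 14 days, one table mandates permanent discontinuation and the other permits a decision to continue. The consequence is possible inconsistent management of a severe toxicity, with a small effect, not derivable from the documents, on a descriptive tolerability comparison. This rests on reading the footnote marker as limiting the clear conflict to Grades 3 and 4, and on finding no statement of precedence in the protocol. It implies nothing about the validity of the PFS analysis, and it takes no position on which clinical rule is right.

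**What to change.** Reconcile footnote 1 of Table 4.2.3.1: 1 with footnote 2 of Table 4.1.4.1.2: 1 so that a single rule governs afatinib after 14 days, stating explicitly whether the clinical-benefit exception applies to diarrhoea. Add to Section 4.2.3.1 the cross-reference to Section 4.1.4 that the skin and mucositis sections already have, or say which table takes precedence. Confirm whether the resulting rule is meant to match the erlotinib exception in Table 4.1.4.2.1: 1, footnote 2. Which rule to adopt is a clinical decision for the sponsor. The cost is footnote wording in a protocol amendment and a note to sites; no analysis or sample-size change is needed.
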